4.4.1.10 Patients will be dosed in cohorts of 5, with a maximum available sample size of 30 early stage and 30 metastatic breast cancer patients. The first cohort of 5 patients will be enrolled at the first reimbursement dose level of \$1000 per month for 4 months (\$4000 per patient in total). Patients will be surveyed biweekly to determine patient financial toxicity (COST tool¹⁹), acceptability of the reimbursement dose (Acceptability of Intervention Measure²⁰), and appropriateness of the reimbursement dose (Intervention Appropriateness Measure²⁰). Participants will be surveyed in-person at baseline, then biweekly over the phone. Semi-structured interviews will be completed in-person, with an option for completion virtually if the participant prefers. At the end of the 4-month period, reimbursement dose suitability will be determined as suitable by a cumulative negative financial toxicity screen and reimbursement dose deemed acceptable and appropriate in at least 4 patients (**Table 2**). If the reimbursement dose is found suitable (all of the 3 criteria are met in at least 4 patients), we will de-escalate the reimbursement dose for the next cohort of 5 patients (**Figure 3**). If the reimbursement dose is found unsuitable (at least 1 of the 3 criteria are not met in 2 patients), the next cohort of 5 patients will be enrolled at the same reimbursement amount (\$1000 per

Table 2. Reimbursement dose suitability and de-escalation criteria.

Reimbursement Dose Suitability Criteria	Instrument	Scoring	De-Escalation Criteria
Negative financial toxicity screen	Comprehensive Score for financial Toxicity (COST) ¹⁹	Scored 0-44, scores < 26 indicate financial toxicity	Average score ≥ 26
Reimbursement dose acceptable	Acceptability of Intervention Measure (AIM) ²⁰	4-item, 5-point Likert scale; higher scores indicate greater acceptability	Average score ≥ 4
Reimbursement dose appropriate	Intervention Appropriateness Measure (IAM) ²⁰	4-item, 5-point Likert scale; higher scores indicate greater appropriateness	Average score ≥ 4

month for 4 months). This sequence will continue until 30 patients have received the reimbursement intervention.

Figure 3. Study schema.

4.4.1.11 Justification of starting dose: The initial \$1,000 dose is based on a prior estimate of a logit model with $\beta_0 = -2.79$ and a slope $\beta_1 = 0.64$ for the dose in \$100 units. This was based on consensus among the investigators in the study and data from three studies:

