- 5.1.1 Sample size: A total of 30 women with early stage breast cancer and 30 women with metastatic breast cancer will be recruited for our study. We will oversample patients who are Black (50%) or residing in rural locations (50%) to ensure representation from patient groups routinely underrepresented in clinical trials. As this is a pilot data funding mechanism, it was necessary to balance both sample size and budgetary constraints. After accounting for research staff (research assistant, biostatistician) and study expenses (interview transcription, publication fees), cohort sizes of 5 were the maximum potential size assuming the potential of no de-escalation of the \$1,000 per month reimbursement constrained within a 2-year timeframe.
- 5.1.2 Power: Because this is a pilot study to assess feasibility of trial-related cost reimbursement to be used in a larger phase II trial, no true power calculation is required.²¹ Feasibility benchmarks will be defined as 80% retention of patients and retained patients completing at least 75% of bi-weekly surveys while enrolled.
- 5.1.3 Analysis: Descriptive sociodemographic, survey, and feasibility data will be calculated for all patients. Comparisons by race (white/black) and residence (rural/urban) will be investigated. Mean differences, or effect sizes, will be calculated using Cohen's d or Cramer's V to determine the magnitude of relationships in bivariate associations.²²

5.2 Aim 2 Analysis: Using a directed content analysis approach,²³ a codebook will be created as guidance. The initial codebook will be reviewed by [name] (*collaborator*, medical oncologist) and [name] (*collaborator*, health economist). Thematic analysis will be conducted by [name] (*PI*) and [name] (*research assistant*, disparities researcher) and used to qualitatively code interview text into codebook categories. Thematic concordance between [name] and [name] will be reviewed after every 2-3 interviews. If needed, new codes or subcodes will be created based on the data. Newly added codes will be used to create a final codebook. All interview transcripts will be reviewed using the final codebook. Themes by race and residence will be investigated.

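### Cramer's V, used in 5.1.3 to size race and residence differences in categorical variables, is unsigned and biased upward at 30 to 60 patients, so its values mislead across variables and hide direction

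*Combined protocol and SAP*

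**What the plan says.** Section 5.1.1 sets the sample: "A total of 30 women with early stage breast cancer and 30 women with metastatic breast cancer will be recruited for our study". It aims for half of the patients to be Black and half to be rural, in order to ensure representation of groups that trials usually miss. Section 5.1.2 states that "no true power calculation is required" because this is a pilot, and gives the feasibility benchmarks, beginning with "Feasibility benchmarks will be defined as 80% retention of patients".

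Section 5.1.3 then says: "Comparisons by race (white/black) and residence (rural/urban) will be investigated". On the measure it says: "effect sizes, will be calculated using Cohen's d or Cramer's V to determine the magnitude of relationships in bivariate associations".

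The section gives no bias correction, confidence interval, test or threshold for reading an effect size. It does not say whether the early stage and metastatic groups are pooled for these comparisons. That V is uncorrected is an inference from this silence, but the ordinary definition of V carries no correction.

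**The concern.** V is the square root of a scaled chi-square statistic. Chance imbalance in either direction pushes it up and nothing pushes it down, so its average under no association is above zero. This holds at any finite sample size. What 30 or 60 patients determine is how large the excess is, and it grows with the number of categories.

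Three things follow if V is read as the magnitude of a relationship:

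- A variable with four levels tends to look more strongly related to race than one with two levels, even if neither is related.
- V has no sign, so it does not show which group had poorer retention or found the reimbursement less suitable.
- No test or interval is planned beside it, so a reader of the results has nothing against which to judge a given V.

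**Working it through.** **Inputs.** n=30 per stage group, or n=60 if pooled (5.1.1). Equal groups, from the 50% targets (5.1.1): 15 v 15 or 30 v 30. Two levels each for race and residence (5.1.3). Retention of 80% (5.1.2) gives n = 0.8 x 30 = 24 or 0.8 x 60 = 48. The plan states no expected V, power or alpha for these comparisons, so it has no figure to reproduce.

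**Formula.** For a 2 x c table, V = sqrt(chi-square / n). With no association, the expected value of V squared is about (c-1)/(n-1).

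- n=30: 1/29 = 0.034, 2/29 = 0.069, 3/29 = 0.103 for c = 2, 3, 4. Square roots: 0.19, 0.26, 0.32.
- n=60: 1/59 = 0.017, 2/59 = 0.034, 3/59 = 0.051. Square roots: 0.13, 0.18, 0.23.

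Mean V lies somewhat below these root-mean-square values. It was obtained by exact enumeration for 2x2 (outcome rates 0.2 to 0.8) and from 200,000 simulated tables per setting for 2x3 and 2x4.

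| Table | Mean V, n=30 | Mean V, n=60 |
|---|---|---|
| 2x2 | 0.147 | 0.103 |
| 2x3 | 0.23 | 0.16 |
| 2x4 | 0.30 | 0.21 |

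At 80% retention the 2x2 means are 0.165 (n=24) and 0.116 (n=48). A 1:2 split instead of 1:1 changes the 2x2 means hardly at all (0.148 and 0.104).

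**Scale for comparison.** Section 2 (Preliminary Studies) reports three Black v White contrasts. In equal groups, V = difference / (2 x sqrt(m(1-m))), where m is the mean of the two rates.

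- 40% v 23%: 0.17 / (2 x sqrt(0.315 x 0.685)) = 0.18
- 32% v 15%: 0.17 / (2 x sqrt(0.235 x 0.765)) = 0.20
- 25% v 10%: 0.15 / (2 x sqrt(0.175 x 0.825)) = 0.20

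So at n=30 an unrelated variable with three or four levels gives on average a larger V (0.23 or 0.30) than these contrasts represent in the population. At n=60 this is true only of the four-level variable, and narrowly (0.21).

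**Signed alternative.** The risk difference averages exactly zero under no association. At a common rate of 0.4 its standard error is sqrt(2 x 0.4 x 0.6 / 15) = 0.18 at n=30 and sqrt(2 x 0.4 x 0.6 / 30) = 0.13 at n=60. The 95% half-widths are about 0.35 and 0.25.

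**Bias-corrected V.** Replace chi-square/n by max(0, chi-square/n - (r-1)(c-1)/(n-1)), use the adjusted dimensions r - (r-1)^2/(n-1) and c - (c-1)^2/(n-1), divide by the smaller of these minus 1, and take the square root. Its null mean at n=30 is about 0.07 (2x2), 0.09 (2x3) and 0.10 (2x4). In 2x2 tables at n=30 with the three contrasts above as the truth (V = 0.18 to 0.20):

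- it averages 0.14 to 0.15, against 0.22 to 0.23 for raw V;
- it is exactly zero in 42% to 46% of samples;
- its root mean square error is 0.16 to 0.17, against 0.14 to 0.15 for raw V.

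**The case against.** A reader might infer that the plan would report race or residence differences most of the time when none exist. The documents do not support that, because 5.1.3 sets no reporting threshold. If V >= 0.1 is assumed as a cut-off, null 2x2 tables reach it in 56% to 59% of samples at n=30 and 43% to 52% at n=60. At an assumed 0.3 the figures are 10% to 12% and 2% to 3%. Only tables with three or more categories give a clear majority at 0.1.

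For binary outcomes much of this is ordinary sampling noise. At outcome rates of 0.4 to 0.5, an absolute risk difference of at least 0.1 arises by chance just as often as V >= 0.1: 58% to 59% at n=30 and 51% to 52% at n=60. Cohen's d behaves alike: with no effect, |d| >= 0.2 occurs in 59% and 44%. This objection stands. The risk difference removes the bias and restores direction, but only the interval shows how little 30 or 60 patients can resolve.

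The reach is also limited. COST, AIM and IAM are judged on average scores (4.4.1.10, Table 2), and Cohen's d, which is signed and centred on zero under no effect, fits them. The feasibility benchmarks are binary per patient, so the larger multi-category values would arise mainly in sociodemographic description. A reader might also infer that oversampling exists to test group differences, or that V feeds the next trial's design. Section 5.1.1 gives representation as the reason. Section 4.4.1.11 says suitability data will inform the next study, but nothing makes a race or residence V a design input. Finally, group percentages may well be reported among the planned descriptive data. The plan does not say that they will accompany V.

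**Conclusion.** The concern holds within a narrow scope. For categorical variables, V as planned has an upward bias that is material at these sample sizes: about 0.15, 0.23 and 0.30 (2x2, 2x3, 2x4) at n=30, and 0.10, 0.16 and 0.21 at n=60. V values should not be ranked across variables with different numbers of categories, and they give no direction. The figures assume roughly equal groups and that V is the ordinary uncorrected statistic. Which sample size applies depends on whether the stage groups are pooled, which 5.1.3 leaves open.

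The consequence is modest. These are exploratory pilot comparisons. The dose decision and the analysis of the three scores are unaffected, and no rate of false reporting can be derived from the plan.

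**What to change.** In 5.1.3:

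1. For binary outcomes (suitability met, patient retained, at least 75% of surveys completed), replace V with the signed risk difference and its 95% confidence interval.
2. For tables with three or more categories, report the percentages by group, raw V, and the bias-corrected V with an interval.
3. State whether the two stage groups are pooled, and give the n behind each estimate.

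The cost is a few sentences and a few lines of code, with no new data. The intervals will be wide, which is a fair picture of the evidence. The corrected V has drawbacks: it is truncated at zero, keeps a small positive null mean (about 0.10 for 2x4 at n=30), and somewhat understates and is noisier for moderate true associations. It should not be used for 2x2 tables, or reported without an interval.
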